Standard Care Arm: Patients will receive prehospital crystalloid infusion or blood component transfusion resuscitation per site standard care for the respective EMS unit/service once all inclusion criteria and no exclusion criteria are met. Once the patient arrives at a participating site and prehospital initiated standard care transfusions are completed, patients will receive standard in-hospital trauma care.

Randomization and Masking: A single stage cluster randomization scheme will be utilized. Participating EMS services/agencies at each site will follow a fixed randomization approach of (LTWB O), (LTWB O), (Standard Care), with the initial treatment being randomly assigned. Thus an EMS service/agency will be randomly assigned to one of three three-month repeated

sequences: (1) LTWB O), (LTWB O), (Standard Care); (2) LTWB O), (Standard Care), (LTWB O); and (3) (Standard Care), LTWB O), (LTWB O)

Communication with the blood bank transportation services and each respective air base or EMS unit/service will occur and an annual schedule of randomization assignment will be distributed to each study site and respective EMS base/service. This specific randomization scheme is required due to the limited supply, goal of minimization of wastage of LTWB O, and the logistics and delivery of the intervention in the prehospital setting. The proposed trial will be an open label trial as blood product transfusion requires appropriate documentation and essential look back procedures.

III. Outcomes

Primary Outcome: The primary outcome for the clinical trial will be all cause 30-day mortality.

30-day mortality will be checked by calling the participant directly with the phone number they provided. If there is no response from the patient, 30-day mortality will be checked by searching public databases such as the National Death Index.

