Inclusion and exclusion criteria will be assessed based on available information at the time of enrollment in the prehospital environment. Although all reasonable efforts will be made by the EMS crews to either directly witness or obtain documentation of eligibility criteria, due to the nature of the emergency pre-hospital setting, there may be occasions where the EMS crew must rely on verbal report of inclusion criteria, including qualifying vitals, from the referring hospital or ground crew. In these instances, if, after subsequent review of outside hospital and/or ground crew documentation, it is determined that the subject did not meet inclusion criteria and/or met exclusion criteria, the subject will remain enrolled in the study based on the intention-to-treat principle.

In the event that a verbal report must be used in lieu of physical documentation or directly witnessing the qualifying vitals, documentation of the verbal report will serve as the source documentation for determining eligibility. Verbal reports will be documented in the emergency medical record and will detail the information reported and by whom.

Study participants will be randomly assigned to either LTWB or standard of care based on a cluster randomized design. Patients will be randomly assigned by EMS base to receive either standard of care (one-month time interval) or LTWB (two-month time interval).

Subjects will undergo initial blood sampling for our secondary outcomes of interest during the first 60 minutes from arrival to the TOWAR trial site. A point of care rapid or conventional thromboelastography (TEG) will be performed for coagulation parameter measurements as close to arrival as possible and as close to 24 hours as possible (+/- 12 hours) when clinical care allows.

V. Potential Risks and Benefits

Potential Risks

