For the primary trial outcome, an indicator of death within 30 days will be generated for each participant. A two-sided z-test for proportions controlling for within cluster correlation utilizing the methods of Donner and Klar will serve as the primary approach to compare the proportions between the treatment arms.²⁴ A mixed-effects logistics regression model will be used to assess the independent impact of LTWB on 30-day survival after controlling for potential confounding effects of baseline characteristics which reveal imbalance between treatment groups. Random effects will be included for intercept, slope, service. Fixed effects will include treatment, baseline characteristics not balanced through random assignment, and month of study.

Analyses to test for the homogeneity of the treatment effect will be carried out for the pre-defined subgroups. Regression models appropriate for the outcome variable (e.g., mixed effect logistic regression for binary outcome variables) will be used to test for the homogeneity of the treatment effect. Main effects will be included in the model for treatment, the indicator of the subgroup and the two-way interaction between treatment and subgroup. If a statistically significant interaction is observed, we will reject the null hypothesis of a homogenous treatment effect.

AIM#2 Analysis: Determine whether prehospital old whole blood (age > 14 days) as compared to young whole blood (age ≤ 14 days) is associated with similar clinical outcomes, hemostasis, prevention of coagulopathy, and platelet function in patients at risk of hemorrhagic shock.

The analysis will begin by describing the baseline demographic and clinical characteristics of the overall population and then stratified by age of whole blood; whole blood age ≤ 14 days versus whole blood age > 14 days. For discrete variables, proportions will be generated, and a chi-square test will be used to test for differences between the proportions. For continuous characteristics, means (medians) and standard deviations (interquartile ranges) will be calculated and t-tests (Wilcoxon) will be used to compare the means (distributions) between treatment arms.

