Sample Size Justification and Power Analysis: The sample size calculations are based on the primary outcome, 30-day mortality, for Aim 1 of the study. With 40 service providers, a sample of 340 participants per treatment group is needed to detect a difference in the 30-day mortality rate of 26% vs. 16% (based on data from the PAMPer study), assuming 80% power, a type I error rate of 0.05, a two-sided alternative hypothesis, and an intraclass correlation coefficient of 0.02, as was observed in the PAMPer study.¹² The size of the ICC will have an impact on the size of the sample needed. If the ICC is smaller (e.g., 0.01 would require a sample size of 300 per arm), fewer people will be needed. However, if it is larger, more will be needed (e.g., 0.05 would require a sample size of 680 per arm).

Using a 2:1 random allocation of study participants to LTWB:standard of care, and enduring that there are 340 participants in the standard care arm, will lead to a total sample size of 1020, with 680 participants receiving LTWB. Assuming that 60% of these participants will receive whole blood \leq 14 days in age and 40% will receive whole blood $>$ 14 days in age, based on a chi-square test of proportions there will be 80% power to detect a higher mortality rate of 22.6% among those receiving whole blood over 14 days old, assuming a 30-day mortality rate of 14% among those receiving whole blood \leq 14 days, a type 1 error of 0.05 and a two-sided alternative hypothesis (that whole blood $>$ 14 days in age has a worse outcome than whole blood \leq 14 days) vs. the null hypothesis that whole blood $>$ 14 days is the same or better than whole blood \leq 14 days).

Randomization of Ineligible Subjects: It is anticipated that there will be a small proportion of patients enrolled who receive whole blood or standard care that in retrospect will not have met the entry criteria and are thus ineligible. In this circumstance, patients will be analyzed according to the group to which they were randomized. Subgroup analyses based on eligibility criteria will be performed if the number of patients so affected is large. However, based on the relatively

limited inclusion and exclusion criteria it is anticipated that the frequency of this event will be low.

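### The primary z-test does not name its cluster or use the fact that every EMS service rotates through both arms; with the service as cluster and a lasting service effect, it is conservative

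*Combined protocol and SAP*

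**What the plan says.** Section VI, AIM#1 Analysis, defines the primary test: "A two-sided z-test for proportions controlling for within cluster correlation utilizing the methods of Donner and Klar will serve as the primary approach". It gives no formula and does not name the cluster. A separate mixed-effects logistic model is planned for covariate adjustment. In that model, "Random effects will be included for intercept, slope, service", with month of study as a fixed effect.

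Section II, Randomization and Masking, describes the allocation. Services "will follow a fixed randomization approach of (LTWB O), (LTWB O), (Standard Care), with the initial treatment being randomly assigned". It continues: "Thus an EMS service/agency will be randomly assigned to one of three three-month repeated" sequences. Section IV, Screening and Enrollment, describes the same split with a different unit: "Patients will be randomly assigned by EMS base to receive either standard of care (one-month time interval) or LTWB (two-month time interval".

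Section VI, Sample Size Justification and Power Analysis, uses a third term: "With 40 service providers, a sample of 340 participants per treatment group is needed to detect a difference" of 26% vs 16%, at 80% power, two-sided 0.05 and an ICC of 0.02. It adds that an ICC of 0.01 would need 300 per arm, while "0.05 would require a sample size of 680 per arm". The 340 is then taken as the standard-care arm of a 2:1 trial, giving 680 + 340 = 1020.

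**The concern.** When the same service treats patients in both arms, whatever is lasting about that service (case mix, transport time, receiving centre) raises or lowers mortality in both arms together and largely cancels in the difference. A cluster-adjusted test for two independent sets of clusters adds the between-service variance in each arm and never subtracts the shared part. Its standard error is then too large. A real mortality benefit could be missed if the true effect is smaller than planned or the ICC is above 0.02. The formal stopping rule also rests on the primary analysis.

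The second problem is the undefined cluster. Service and service-month give different standard errors. In an open-label trial that choice should not remain open once data exist.

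**Working it through.** **1. Reproduce the stated sample size.** Inputs from the sample size section: 26% vs 16%, two-sided 0.05, 80% power, 40 services.

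n0 = (1.96 + 0.8416)² × (0.26×0.74 + 0.16×0.84) / 0.10² = 256.5 per arm without clustering.

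With k clusters per arm, n = n0(1 − ICC) / (1 − n0×ICC/k).

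| ICC | Stated | k = 20 per arm | k = 40 in each arm |
|---|---|---|---|
| 0.01 | 300 | 291 | 271 |
| 0.02 | 340 | 338 | 288 |
| 0.05 | 680 | 679 | 359 |

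Rounded up to whole cluster sizes (multiples of 20), the k = 20 column gives exactly 300, 340 and 680. A pooled variance (n0 = 260) misses the third figure (706). A continuity correction (n0 = 279) does not match all three with either k. The trial was therefore sized as a parallel design with 20 services per arm.

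**2. Standard error under the rotating design.** Assume 40 equal services, each with 340/40 = 8.5 standard-care and 680/40 = 17 whole-blood patients, the service as cluster, and a service effect fully shared by both arms.

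- Test variance = 0.1924(1 + 7.5×ICC)/340 + 0.1344(1 + 16×ICC)/680
- Actual variance = test variance − 2×ICC×√(0.1924×0.1344)/40

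ICC 0.02: 0.000651 + 0.000261 = 0.000912; less 0.000161 = 0.000751. SE 0.0302 against 0.0274, ratio 1.10.

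ICC 0.05: 0.000778 + 0.000356 = 0.001134; less 0.000402 = 0.000732. SE 0.0337 against 0.0271, ratio 1.24.

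**3. Type I error.** With equal mortality in both arms, the variance ratio at ICC 0.02 is [1.32/680 + 1.15/340] / [0.98(1/680 + 1/340)] = 1.23, an actual level of 3.0%. At ICC 0.05 it is 1.60, or 1.3%.

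**4. Power.** Current test: Φ((d − 1.96×SE_test)/SE_actual). Test with the correct SE: Φ(d/SE_actual − 1.96). The 18% rate is an assumption; it is not in the documents.

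| Effect | ICC | Correct SE | Current test |
|---|---|---|---|
| 26% vs 16% | 0.02 | 95.4% | 93.2% |
| 26% vs 16% | 0.05 | 95.9% | 89.6% |
| 26% vs 18% | 0.02 | 82% | 76% |
| 26% vs 18% | 0.05 | 83% | 68% |

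**5. Simulation.** 40 services, 48 months, randomly started three-month sequences, Poisson accrual, ANOVA estimate of the ICC; 8,000 null trials (20% mortality) and 4,000 trials at 26% vs 16% per scenario. Service as cluster, equal sizes, ICC 0.02 / 0.05:

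| Service effect | SE too large by | Type I error |
|---|---|---|
| Persistent, shared by both arms | 10% / 24% | 2.7% / 1.5% |
| Half persistent | 5% / 13% | 3.7% / 2.9% |
| Month-only correlation | 0–4% | 4.2–4.7% |
| Independent in the two arms | none | 5.1–5.6% |

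With unequal service sizes the first row is 2.6% / 1.1%. Simulated power at 26% vs 16%, current test against a service-stratified t-test, was 93.6% vs 94.1% (ICC 0.02) and 89.3% vs 95.0% (ICC 0.05).

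**6. Service-month as cluster.** There are 1020/(40×48) = 0.53 patients per cluster, so the correction nearly vanishes. Type I error was 4.2–5.0% with a shared service effect. With independent service effects by arm, an extreme case, it was 7.4% (ICC 0.02) and 11.1% (ICC 0.05).

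The service-stratified t-test ran at 4.3–6.0% in all 16 null scenarios.

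**The case against.** The plan gives no formula, so the version for two independent sets of clusters is an inference. The cluster can largely be read as the service: that is the randomised unit, the ICC is attached to 40 service providers, and the supporting model has a service term. Service-month is an unlikely reading.

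Conservatism also needs service effects that persist and are shared by both arms. Standard care differs by service, so the treatment effect may differ too. In simulation with an assumed between-service SD of 10 percentage points in the treatment effect, type I error was 4.8% at ICC 0.02: the conservatism disappears. At the plan's own inputs the power loss is small. Using the final-analysis boundary of 1.993 instead of 1.96, power is still about 93% (ICC 0.02) and 89% (ICC 0.05), by a single-look approximation. Sizing as a parallel design errs towards too many patients, and a within-service model will be reported anyway.

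Most of this stands as limits on the size of the problem. It does not remove it. The parallel-design sample size makes the two-sample reading the natural one. The mixed model is only supporting. Varying treatment effects argue for a robust within-service test, not for the current one: with the same SD and no underlying service effect, the current test ran at 7.4%.

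**Conclusion.** The concern holds. The primary test leaves its cluster undefined, does not use the within-service comparison that the rotation provides, and is paired with a sample size for a design the trial does not use. If the service is the cluster, the standard two-sample adjustment is applied and service effects persist in both arms, the p value and confidence interval are conservative by the amounts shown; the estimate is unbiased and false positives do not rise. The inflation shrinks as persistence falls. This does not threaten validity at the planned effect. It costs sensitivity at smaller effects or higher ICCs, and it should be settled before any unblinded comparison.

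**What to change.** In the SAP, define the cluster and the period, and use one name for the randomised unit throughout. Make the primary test a within-service comparison, in one of two forms:

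- a service-stratified (Mantel-Haenszel) risk difference with a cluster-robust standard error and a t reference on services minus 1 degrees of freedom; or
- a mixed model with service and service-by-period effects, reporting its marginal risk difference.

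Keep the current z-test as a sensitivity analysis, and restate power for the rotating 2:1 design.

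The cost is SAP wording and a new power statement; service and month are already in the planned model. There are two small downsides. Without the small-sample correction the stratified test is slightly liberal (4.9–6.8% in simulation). If service effects do not persist across months, stratifying costs about 2 power points (93.9% vs 95.7% at ICC 0.02; 93.0% vs 94.9% at ICC 0.05). The robust standard error matters: a Mantel-Haenszel test with its usual variance ran at about 9% when the treatment effect varied between services (SD 10 points), while the robust t-test held 4.6–5.4% in null cases that included varying effects.

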An unadjusted analysis comparing the 30-day mortality rate by blood age will be conducted using a chi-square test. Additionally, because of the observational nature of the study, a propensity adjusted analysis will be carried out to control for potential confounders (including biological sex, TBI, etc.). A generalized boosted regression model (GBM) will be used to generate a propensity score for each participant indicating the probability of receiving young whole blood. The GBM approach will be used to identify important characteristics that will be used to estimate the propensity scores. From this approach, a propensity score, $p(x)$, indicating the probability of receiving young whole blood given the observed characteristics will be obtained for each subject.

We will use the Toolkit for Weighting and Analysis of Nonequivalent Groups (twang) software package and the SAS/Stata macros (<http://www.rand.org/statistics/twang/downloads.html>) to estimate and evaluate the propensity scores. We will estimate the propensity score for each

subject by running the macro or command *ps* (dichotomous) or *mnp* (multinomial). That is, GBM will fit separate GBMs to each dummy treatment indicator to estimate the propensity score for the given phenotype. We will consider all the subject characteristics when fitting GBM. The GBM approach will select which characteristics to include and the best functional form including interactions. If missing data is present for the subject characteristics, twang will attempt to construct weights that also balance rates of missingness by creating indicator variables.

The maximum number of iterations for the GBM approach will be set to the default (i.e. 10000). The optimal number of iterations will be selected as the one that minimizes the balance statistics of interest. We will use the balance statistics *es.mean* and *ks.mean*. The *es.mean* uses the absolute standardized bias (also referred as the effect size or absolute standardized mean difference) and summarizes across variables, and the *ks.mean* uses the KS statistic to assess balances and summarizes across variables. We will allow a maximum of three splits for each tree in the model, allowing for three-way interactions between all covariates to be considered. The shrinkage parameter will be set to 0.0005 to ensure a smooth fit. The tuning parameters involved in the GBM models will be adjusted if necessary, until covariate balance is achieved.

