A similar approach will be taken for the secondary outcomes, though the analytic approach may vary based on the distribution of the outcome. For example, for a continuous secondary outcome (e.g., clotting time parameters); a mixed-effects linear regression model to estimate the independent effect of the age of whole blood on the outcome. For time to event outcomes (e.g., time to death), Kaplan-Meier curves will be generated for each treatment group and a log-rank test will be used to compare the distribution of the cumulative proportion. Observations will be censored at 30 days after arrival. A multivariable analysis of survival with the use of a Cox

proportional-hazard with shared frailty model to evaluate the treatment effect with adjustment for possible confounding factors and site clustering on survival.

AIM#3 Analysis: Determine whether prehospital low titer whole blood as compared to standard prehospital resuscitation results in lower early mortality endpoints, blood and blood component transfusion requirements, lower incidence of coagulopathy, and improved hemostatic and platelet function in patients at risk of hemorrhagic shock.

The analysis of the secondary outcome will mirror the analytic approach for Aim 2. The analytic approach for other binary outcomes (e.g., 6-hour mortality) will be identical as those for the primary analysis. For continuous outcomes (e.g., 24-hour blood and component transfusion requirements), a mixed effect regression model will be used to determine if the average number of units transfused between the two treatment groups differ. For time to event outcomes (e.g., time to hemostasis), Kaplan-Meier curves will be generated for each treatment group and a log-rank test will be used to compare the distribution of the cumulative proportion. A multivariable analysis of survival with the use of a Cox proportional-hazard with shared frailty model to evaluate the treatment effect with adjustment for possible confounding factors and site clustering on survival.

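### The secondary analyses do not follow the EMS service as the clustering unit, and the consequence falls mainly on the blood-age comparison and its stated power

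*Combined protocol and SAP*

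**What the plan says.** **Unit of randomisation.** Under Randomization and Masking (section II): "Participating EMS services/agencies at each site will follow a fixed randomization approach". Each service rotates through two LTWB months and one standard-care month: "Thus an EMS service/agency will be randomly assigned to one of three three-month repeated" sequences. Section IV describes the unit as the base: "Patients will be randomly assigned by EMS base to receive either standard of care".

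**Primary analysis (section VI, AIM#1 Analysis).** A z-test adjusted for within-cluster correlation by the Donner and Klar method, with a supporting mixed logistic model that has a random effect for service. The sample size paragraph uses 40 service providers and an ICC of 0.02.

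**Secondary analyses (section VI, AIM#2 and AIM#3 Analysis).**
- Blood-age mortality: "An unadjusted analysis comparing the 30-day mortality rate by blood age will be conducted using a chi-square test". A propensity-weighted mixed log-binomial model follows. Its random-effect unit is not named, and its propensity model lists site but not service.
- Time-to-event outcomes, in both aims: "a log-rank test will be used to compare the distribution of the cumulative proportion", then a shared-frailty Cox model with "adjustment for possible confounding factors and site clustering on survival".
- Continuous outcomes: mixed models, again with no unit named.
- Aim 3 opens with "The analysis of the secondary outcome will mirror the analytic approach for Aim 2". The sentences after it give each outcome type its own method, and binary outcomes take the primary analysis method.

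**Blood-age power (Sample Size Justification and Power Analysis).** 680 LTWB patients split 60:40, chi-square test, 80% power for 22.6% against 14%. No ICC appears in this statement.

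**The concern.** Patients of one service share crews, territory and stock, and the plan accepts an outcome correlation of 0.02 within service. A test that treats them as independent is valid only if the compared groups are balanced within services. The randomised arms are close to that by design. Blood age is not: it is not randomised, units are held at an EMS base or stocking facility, and shelf life is 21 or 35 days depending on the site's process. If some services mostly give older blood, the plain chi-square and log-rank tests produce p-values that are too small. A site frailty does not absorb differences between services of the same site, of which there are 40/10 = 4 on average.

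The stakes are moderate. The primary test is untouched. But section III makes blood age the principal secondary outcome, and under Interim Analyses the DSMB is to weigh the agreement of primary and secondary results. The sentence tying Aim 3 to Aim 2 also leaves unclear whether any of the observational method is meant for a randomised comparison.

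**Working it through.** **1. Which cluster the plan's sizing uses.** Inputs from the sample size paragraph: 26% vs 16%, 80% power, two-sided 0.05, 40 services. The unpooled two-proportion size is n0 = 256.5 per arm. With k = 20 services per arm, n = n0(1 − ICC)/(1 − n0·ICC/k), rounded up to whole patients per cluster:

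| ICC | Calculation | n | Rounded | Plan |
|---|---|---|---|---|
| 0.01 | 253.9/0.8718 | 291.3 | 300 | 300 |
| 0.02 | 251.4/0.7435 | 338.1 | 340 | 340 |
| 0.05 | 243.7/0.3588 | 679.2 | 680 | 680 |

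All three figures match, so the plan's own arithmetic treats the service as the cluster.

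**2. The blood-age power statement.** Groups: 0.6 × 680 = 408 young, 0.4 × 680 = 272 old; rates 14% and 22.6%. The pooled rate is 0.1744. The null SE is 0.0297 and the alternative SE is 0.0306. Power = Φ((0.086 − 1.96 × 0.0297)/0.0306) = 81.8%. This agrees with the stated 80%, but only with no design effect.

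**3. Type I error of the blood-age chi-square.** There are 680/40 = 17 LTWB patients per service. If a share s of the blood-age variation lies between services, the variance is inflated by about D = 1 + (17 − 1) × ICC × s. The true error of the nominal 5% test is 2(1 − Φ(1.96/√D)). The share s is not in the documents, so a range is shown.

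| s (assumed) | D at ICC 0.02 | Error | D at ICC 0.05 | Error |
|---|---|---|---|---|
| 0 | 1.00 | 5.0% | 1.00 | 5.0% |
| 0.2 | 1.064 | 5.7% | 1.16 | 6.9% |
| 0.5 | 1.16 | 6.9% | 1.40 | 9.8% |
| 1 | 1.32 | 8.8% | 1.80 | 14.4% |

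A beta-binomial simulation (40 services of 17, 16% mortality, 40% old blood, no true effect, 40,000 replicates per setting) gives 5.7%, 7.1% and 8.9% at ICC 0.02, and 6.9%, 9.8% and 14.3% at ICC 0.05, for s = 0.2, 0.5 and 1. A second simulation with services of unequal size and 20% mortality gives 4.5% to 9.6% at ICC 0.02 for blood-age clustering of 0 to 0.9, and 5.0% to 16.2% at ICC 0.05. Unequal services can therefore push the error somewhat above the equal-size figures.

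**4. Blood-age power with clustering.** Dividing the group sizes by D:

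| D | Power for 22.6% vs 14% | Rate detectable with 80% power |
|---|---|---|
| 1.00 | 81.8% | 22.4% |
| 1.16 | 76.0% | 23.1% |
| 1.32 | 70.6% | 23.8% |
| 1.80 | 57.6% | 25.6% |

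D = 1.32 is the upper bound at the plan's ICC; D = 1.80 is the upper bound at ICC 0.05.

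**5. LTWB versus standard care.** 4,000 null trials per setting were simulated: 1020 patients, 40 unequal services, the rotating 2:1 sequence, 20% mortality, and a plain chi-square on death standing in for the log-rank. Rejection was 4.9% to 5.3% at ICC 0.02 and 5.3% to 5.8% at ICC 0.05. The Monte Carlo standard error is √(0.05 × 0.95/4000) = 0.3 points. Rotation within service removes nearly all the inflation.

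**The case against.** - *The unadjusted tests are only a first step.* This stands in part. A reader might infer that the secondary analyses disregard clustering altogether. They do not: the chi-square is followed by a weighted mixed model and each log-rank by a frailty model. But those models do not settle the matter as written, because one names site and the other names no unit.
- *Aim 3 is not really told to use the observational method.* This largely stands. A reader might infer from the opening sentence that propensity weighting is prescribed for the randomised comparison, in conflict with the primary method. The sentences that follow specify a method for each outcome type, and none contains a propensity step. The opening sentence may refer only to model families, or, being singular, to blood age as the principal secondary outcome. It is an ambiguity to be settled in wording, not two firm and incompatible instructions.
- *Clustering of blood age by service is not documented.* This stands. The only structural source in the documents is shelf life, which varies by site, so a site term has some rationale in Aim 2. At s = 1 each service would have to give one age class throughout enrolment, which nothing supports. The 9% and 14% figures are bounds, not estimates.
- *Confounding is the larger threat to a non-randomised comparison.* True, and the plan addresses it, but weighting for confounders does not correct the standard error for correlation within service.

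**Conclusion.** The point holds as a mismatch between the unit of randomisation, sizing and primary analysis (service) and the unit used or left unstated in the secondary analyses. Its weight is on blood age. At ICC 0.02 the unadjusted chi-square has a true error of about 5% to 7% for s between 0 and 0.5, with an upper bound of about 9% (about 14% at ICC 0.05). Power is 81.8% with no clustering and as low as 70.6% at the upper bound for ICC 0.02. These figures assume 17 LTWB patients in every service, the plan's ICC applied within service, and no further correlation between services of one site. The bounds move up modestly if services differ in size. If blood age varies only within services, the inflation disappears.

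A reader might also infer that the p-values for LTWB versus standard care are materially wrong. The rotating design does not support that: the effect on type I error is negligible, and aligning the unit there is a matter of consistency. The primary analysis is not affected.

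**What to change.** 1. Put the Cox shared frailty and the Aim 2 random effect on service, nested in site, and name the unit in the other mixed models. Use one term for the randomised unit, since section II says service or agency and section IV says base.
2. Stratify the log-rank by service for LTWB versus standard care. With 1020/40 = 25.5 patients per service, about 17 and 8.5 by arm, little information should be lost, though this was not computed.
3. Replace the plain chi-square for blood-age mortality with a service-clustered test. For blood-age survival, let the service-frailty Cox model carry the inference: stratification would discard services that give mostly one age class.
4. State that the blood-age power assumes no clustering, and give the range: 81.8% down to 70.6% at ICC 0.02, depending on the share of blood-age variation between services.
5. Reword the opening sentence of the Aim 3 analysis so that propensity weighting applies only to blood age and LTWB versus standard care follows the clustered Aim 1 approach. Simply changing the aim number would not do, because if the sentence was meant for blood age it would send that comparison to the wrong method.

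The cost is SAP wording, with the same data and software. The one real downside is a less favourable power figure for the blood-age comparison.
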